2.2. Background

AD is a progressive neurodegenerative disorder affecting wide areas of the cerebral cortex and hippocampus. Even though psychopathology of AD can differ greatly from one person to another, it includes both behavioral and psychological symptoms that are common and associated with distress for patients and caregivers, greater risk of institutionalization, and accelerated progression to severe dementia and death. The three most common psychopathologies in AD are agitation, depression and affective symptoms, and psychosis (Tractenberg 2003b). Additionally, sleep and circadian rhythm disturbances are frequent in AD, and it has been reported that up to 45% of patients may have sleep issues (Moran 2005; Pistacchi 2014; Cipriani 2015). The most frequent sleep disturbances include excessive awakenings (23%), early morning awakening (11%), excessive daytime sleepiness (10%), and napping for more than 1 hour during the day (14%) (Vitiello 2001). Sleep in AD is often fragmented with patients often having reduced total sleep times at night leading to significant sleep periods during the day. Such disturbances can appear early in the course of the disease, and they tend to be correlated with the severity of the cognitive decline and behavioral and psychological symptoms (Moran 2005).

Seltorexant is a potent and selective antagonist of the human orexin-2 receptor (OX2R) and is currently being developed by Janssen Research & Development for the adjunctive treatment of major depressive disorder with IS (MDDIS) and for the treatment of Behavioral and Psychological Symptoms of Dementia (BPSD). In addition to a hypothesized role in modulating arousal, the sleep- and mood-enhancing effects of a selective OX2R antagonist, such as seltorexant, are expected to confer benefit in mood disorders and neurodegenerative diseases.

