In adults, the benefits of seltorexant for MDD include symptoms beyond sleep. In the clinical studies in adults conducted to date in the MDD study population, clinically and statistically significant changes in the core symptoms of depression (HDRS-6 or MADRS-6) have been seen, which may indicate that seltorexant will help with some of the symptoms of BPSD such as apathy and depression. Further, seltorexant 20 mg has consistently shown a greater benefit in patients with at least moderate IS in patients with MDD. However, it is not known if the presence of IS (as assessed by the sleep disorder inventory [SDI]) will predict efficacy in BPSD. In this study, both patients with and without sleep problems will be included.

For the elderly, the pharmacokinetics are similar in the elderly and adults (42847922EDI1014). In terms of safety, elderly and adults were included in the insomnia study 42847922ISM2005 with both populations having fewer adverse events with seltorexant than with placebo or zolpidem including no cases of somnolence in the elderly population. In that study, postural stability was

studied at 4 hours after dosing (waking the participant up in the middle of the night) and the next morning with no differences between patients treated with seltorexant or placebo.

To ensure safe use of study intervention, besides routine safety monitoring and participant management, this protocol also includes specific risk mitigation strategies, including: restrictions on driving, operating machinery, engaging in hazardous activity when participants have had insufficient sleep or are feeling sedated the next day (Section 5.3, Lifestyle Considerations; and frequent assessments at the site (every 1-2 weeks), paying special attention to clinically significant AEs that are known to have been reported with drugs of the same pharmacological class (Section 8.4.6, Adverse Events of Special Interest), reducing suicidality risk inherent in the underlying depression by excluding high risk participants, and performing Columbia Suicide Severity Rating Scale (C-SSRS) prior to dosing and at each study visit. Further, due to the impairments associated with AD, all participants must have a study partner to help with the procedures of the protocol and to provide additional feedback about any issues related to the study treatment.

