5.4.1.2.2. Analysis Methods

The change from baseline in SDI average total score and SDI summed product score will be analyzed using the same MMRM model as described for the NPI-C A+A score, with baseline SDI Average Total score and baseline SDI Summed Product score, respectively, as the covariate. Comparison between seltorexant and placebo at Day 43 will be performed using the appropriate contrast. Difference in least square means and 2-sided 80% CI will be presented.

Descriptive statistics of the actual values and the change from baseline(DB) to each postbaseline time point will be presented for SDI average total score and SDI summed product score by intervention group.

Least squares mean changes from baseline(DB) (+/- SE) will be presented graphically over time.

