5.5.7.2. Analysis

Descriptive statistics of the patient-reported GDSI total score at baseline(DB) and endpoint (DB), as well as the change from baseline to Endpoint (DB), will be presented by intervention group.

An ANCOVA model will be used to test the difference of change from baseline at endpoint(DB) in GDSI total score between seltorexant and placebo. The model will include intervention and baseline NPI Sleep domain score category (per eDC) as factors, and baseline(DB) GDSI total score value as a covariate. Difference of least square means and 2-sided 80% CI will be presented.

5.5.8. The association between treatment effect of seltorexant in sleep and treatment effect in agitation/aggression

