5.5.8.1. Analysis

Correlations between change in NPI-C A+A score and change in SDI average total score and between change in NPI-C A+A score and change in SDI summed product score over time will be explored; Pearson and Spearman correlation coefficients will be calculated. Scatter plot of change in scores of the 2 assessment scales over time will be presented for each intervention group.

A mediation analysis will be performed to examine the mediating role of improvement in sleep assessed by change from baseline in SDI score on change from baseline in NPI-C A+A score provided that both endpoints demonstrate a statistically significant difference between seltorexant and placebo. This analysis will assess the extent to which change in NPI-C A+A score may be mediated by or independent of change in SDI score based on observed data (i.e., data collected at each time point without carrying forward previous values) at Day 43. The analysis will consider both change in NPI-C A+A score and change in SDI score as continuous variables.

• Simulation-based Counterfactual Approach: this analysis introduced by Imai et. al obtains the natural direct effect and natural indirect effect using numerical simulations. The approach uses parametric bootstrapping to construct the point estimate and its uncertainty estimates for direct effect and indirect effect from the bootstrap sampling distribution. For each bootstrapped sample, change from baseline in NPI-C A+A score and change from baseline in SDI score will be analyzed. The ANCOVA analysis of change in NPI-C A+A score from baseline will include factors for treatment (placebo and seltorexant dose groups), change from baseline (Day 1, predose) in SDI score, treatment-by-change from baseline in SDI score

Statistical Analysis Plan 42847922ALZ2001

interaction if the interaction is significant, and baseline NPI-C A+A score as a covariate. The ANCOVA analysis of change in SDI score will include factors for treatment (placebo and seltorexant dose groups), and baseline NPI-C A+A score as a covariate. Estimate of the controlled direct effect will be obtained by plugging in the estimated coefficient values and the mean level of change in SDI score into the analytic expressions.

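### The exploratory mediation models leave out baseline SDI, so the split of the agitation effect into direct and sleep-mediated parts can be biased in either direction

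*SAP*

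**What the plan says.** SAP 5.5.8.1 plans a simulation-based analysis of natural direct and indirect effects, with two ANCOVAs fitted at Day 43.

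- **Outcome model.** It opens "The ANCOVA analysis of change in NPI-C A+A score from baseline will include factors for treatment (placebo and seltorexant dose groups), change from baseline", the change being that in the SDI score. It ends with a treatment-by-SDI-change "interaction if the interaction is significant, and baseline NPI-C A+A score as a covariate".
- **Mediator model.** "The ANCOVA analysis of change in SDI score will include factors for treatment (placebo and seltorexant dose groups), and baseline NPI-C A+A score" as the covariate.
- **Gate.** The analysis is run "provided that both endpoints demonstrate a statistically significant difference between seltorexant and placebo".

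Both term lists are closed, and neither contains baseline SDI or the baseline NPI sleep category. The section states no assumption about mediator-outcome confounding and plans no sensitivity analysis for it.

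Elsewhere the SAP does use these covariates. The secondary analysis of the same SDI changes (5.4.1.2.2) is fitted "with baseline SDI Average Total score and baseline SDI Summed Product score, respectively, as the covariate". The primary MMRM (5.3.2.1.1) includes the baseline sleep category. So does the GDSI ANCOVA (5.5.7.2): "The model will include intervention and baseline NPI Sleep domain score category (per eDC) as factors". The MMSE analysis (5.5.9.2) reuses that ANCOVA.

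**The concern.** The mediator is a change score, so its own baseline is almost certain to predict it. Leaving baseline SDI out of the mediator model costs only precision, because treatment is randomised.

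The outcome model is different. Nobody is randomised to a level of SDI change, so the slope of A+A change on SDI change is an observational association. If baseline SDI predicts A+A change given treatment, SDI change and baseline A+A, that slope absorbs part of its influence. Whatever is wrongly added to the indirect effect is taken from the direct effect; the total is unchanged. If baseline SDI acts on A+A only through SDI change, there is no confounding.

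The direction depends on the sign. If participants with worse baseline sleep improve more on A+A, the planned models can create a sleep-mediated benefit. If they improve less, the models can hide one.

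The protocol does not settle the question. Section 2.2 says of sleep disturbances that "they tend to be correlated with the severity of the cognitive decline and behavioral and psychological symptoms", which makes a link plausible. Section 2.3 says "it is not known if the presence of IS (as assessed by the sleep disorder inventory [SDI]) will predict efficacy in BPSD". The analysis serves a listed exploratory objective, namely whether the agitation effect is associated with the sleep effect, so its answer could shape how the drug's action is described.

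**Working it through.** **The plan's own figures.** The SAP gives no figure for the mediation analysis. Its sample size reproduces: 2 × (1.2816 + 0.8416)² × (10/5)² = 36.06, so 37 per arm and 74 in total. With 43 × 0.85 = 36.55 completers per arm, power is 80.4% at one-sided 0.1. The 86 enrolled therefore leave about 86 × 0.85 = 73 completers, the size used below.

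**Inputs**
- From the documents (SAP Section 3): difference 5 points, SD 10, 86 participants, 15% drop-out.
- Assumed: true indirect effect 0; treatment shifts SDI change by d = 0.5 SD; baseline SDI correlates −a with SDI change, a = 0.4 to 0.6; baseline SDI correlates r = 0.3 with baseline A+A; baseline SDI affects A+A change by g SD per SD, |g| = 0 to 0.3, given treatment, SDI change and baseline A+A.

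**Closed form.** The omitted-variable bias in the SDI-to-A+A slope is g × cov(SDI₀, ΔSDI | T, A+A₀) / var(ΔSDI | T, A+A₀). In standardised units the covariance is −a(1 − r²) and the variance is 1 − a²r². Multiplying by d and by the SD of 10 gives

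|spurious indirect effect| = d × 10 × |g| × a(1 − r²) / (1 − a²r²).

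Worked case, a = 0.6, r = 0.3, |g| = 0.3: 0.5 × 10 × 0.3 × 0.6 × 0.91 / 0.9676 = 0.846 points, and 0.846 / 5 = 17%.

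| \|g\| | a = 0.4 | a = 0.6 |
|---|---|---|
| 0 | 0 | 0 |
| 0.1 | 0.185 | 0.282 |
| 0.2 | 0.369 | 0.564 |
| 0.3 | 0.554 | 0.846 |

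The largest value becomes 0.90 if r = 0 and 0.74 if r = 0.5.

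**Trial-size simulation with the gate.** There were 6,000 trials per scenario, with n = 73, direct effect −5 points, baseline A+A effect −0.3 SD per SD (assumed) and no interaction. The gate was two-sided p < 0.20 in the direction of improvement on both endpoints. SAP 5.5.8.1 names no threshold, so 0.20 is taken from SAP Section 2. The gate was met in 68–77% of runs. Negative values mean improvement.

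| Scenario | Mean spurious indirect effect, planned models | 80% interval excludes zero |
|---|---|---|
| g = 0 | 0.00 | 15–16% |
| g = 0.2, a = 0.4 | 0.40 | 23% |
| g = +0.3 / −0.3, a = 0.6 | +0.87 / −0.93 | 44–50% |

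With baseline SDI added to both models, the interval excludes zero in 17–19% of runs, against a nominal 20%. The gate does not remove the bias.

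**When some mediation is real.** In a second illustration all inputs are assumed and standardised: treatment effect on SDI −0.4, SDI-to-A+A slope 0.30, direct effect −0.35. The true indirect effect is −0.4 × 0.30 = −0.12, and the true share mediated is 0.12 / 0.47 = 25.5%. The planned models give about 37% when the baseline SDI effect is −0.30, 25–26% when it is 0, and about 14% when it is +0.30. Adding baseline SDI to both models returns about 25% in every case.

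**Precision.** Adding baseline SDI lowers the residual variance of SDI change by 1 − (1 − a²)/(1 − a²r²): 14.8% at a = 0.4 and 33.9% at a = 0.6.

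**The case against.** The strongest reply is that the bias is possible rather than shown, and matters only for a fairly large g.

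- **Evidence for the condition is thin.** Protocol 2.2 describes a link with symptom severity, and both models already adjust for baseline A+A. Protocol 2.3 is about predicting efficacy, which is effect modification and not the prognostic path that would confound the slope. Both points stand; neither passage shows the condition is absent.
- **The comparison with other SAP models is loose.** Baseline SDI in 5.4.1.2.2 sharpens a randomised contrast, and the sleep category is a stratification factor. Neither was chosen to control mediator-outcome confounding. This is fair: the comparison shows an unexplained difference and that the covariates are to hand, no more.
- **Small g.** At |g| = 0.1, with the same set-up and gate, the spurious effect is 0.18–0.31 points and the 80% interval excludes zero in 17–20% of runs. Root mean square error is then lower without baseline SDI (about 0.71–0.73 points) than with it (0.73–0.80). This stands. Clear inflation appears from |g| = 0.2 with a = 0.6 (32%). At |g| = 0.3, baseline sleep is as strong a predictor as baseline A+A is assumed to be.
- **The fix is partial.** Other confounders may remain. The sleep category overlaps with SDI, which expands the same NPI-12 item, and adds almost nothing beyond it. This too stands, and is why a sensitivity analysis is proposed.

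None of this supplies the missing term or a reason for leaving it out. A direct/indirect split is interpretable only if mediator-outcome confounding is dealt with, and here the most obvious candidate is already measured.

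**Conclusion.** The concern holds, as a minor point. Baseline SDI is absent from both mediation models. If it predicts A+A change beyond treatment, SDI change and baseline A+A, the indirect effect is biased, and the direct effect is biased by the same amount in the opposite direction.

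Under the assumptions above, the size runs from 0 to about 0.85 NPI-C points (17% of the planned 5), with either sign. The quantities that drive it (g, the correlation of baseline SDI with SDI change, and the treatment shift in SDI) are assumed, so the true size is unknown and may be nil. Confidence is medium for that reason.

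The analysis is exploratory and runs only if both endpoints are significant. The total treatment effect and the primary, secondary and safety results are unaffected.

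**What to change.** In SAP 5.5.8.1, add two covariates to both the mediator and the outcome ANCOVA:

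- the baseline SDI score matching the mediator in use (average total or summed product);
- the baseline NPI sleep domain category per eDC.

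Then add a sensitivity analysis over an assumed residual correlation between the errors of the two models, since other mediator-outcome confounders, such as cognitive severity or permitted rescue use, may remain. Report the split as exploratory.

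The cost is SAP wording and one or two degrees of freedom per model. No new data are needed, because SDI is collected at Visit 2. If baseline SDI turns out unrelated to A+A change, the indirect estimate is somewhat noisier: its simulated SD rises from 0.69 to 0.76 points at a = 0.4, and from 0.68 to 0.82 at a = 0.6. The simulations added baseline SDI only; the figures do not include the sleep category.

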5.5.9. Cognitive Symptoms

5.5.9.1. Definition

The Alzheimer's Disease Assessment Scale Cognitive subscale 14-item version (ADAS-Cog-14) is a rater administered instrument that was designed to assess the severity of dysfunction in cognition characteristic of persons with AD (Rosen 1984). The ADAS-Cog-11 consists of 11 tasks measuring the disturbances of memory, language, praxis, attention, and other cognitive abilities, which are often referred to as the core symptoms of AD.

The modified ADAS-Cog 14-item scale includes all original ADAS-Cog items with the addition of a number cancellation task, Maze task and a delayed free recall task, for a total of 90 points, with higher scores indicative of worse cognitive performance.

The Mini-Mental State Examination (MMSE) is a 30-point questionnaire that is used extensively in clinical and research settings to measure cognitive impairment. It is commonly used in medicine and allied health to screen for dementia. The test is divided into two sections: the first section requires vocal responses and covers orientation, memory, and attention. The second part tests ability to name, follow verbal and written commands, write a sentence spontaneously, and copy a complex polygon similar to a Bender- Gestalt Figure. The score ranges from 0 (minimum score) to 30 (maximum score) and it is calculated by the sum of the sub-items scored 0 (incorrect answer) or 1 (correct answer) (Creavin 2016; Folstein 1975).

5.5.9.2. Analysis

The change from baseline in ADAS-Cog-14 total score will be analyzed using the same MMRM model as described for the NPI-C A+A score, with baseline ADAS-Cog-14 total score as the covariate. Comparison between seltorexant and placebo at Day 43 will be performed using the appropriate contrast. Difference in least square means and 2-sided 80% CI will be presented. Descriptive statistics of the actual values and the change from baseline(DB) to each postbaseline time point will be presented for ADAS-Cog-14 total score by intervention group.

Least squares mean changes from baseline(DB) (+/- SE) will be presented graphically over time.

The change from baseline in MMSE total score will be analyzed using the same ANCOVA model as described for the GDSI score, with baseline MMSE total score as the covariate. Comparison between seltorexant and placebo at Day 43 will be performed using the appropriate contrast. Difference in least square means and 2-sided 80% CI will be presented.

Descriptive statistics of the actual values and the change from baseline(DB) to each postbaseline time point will be presented for MMSE total score by intervention group.

5.5.10. Subgroup Analyses

For the subgroups listed in Section 5.7.4, subgroup analyses using MMRM will be performed for the change in NPI-C A+A total score at Day 43. The fixed terms in the model will be intervention group, baseline NPI-12 sleep domain score category (<4, ≥4) per eDC, time, subgroup, time-by-intervention interaction, intervention-by-subgroup interaction, and time-by-intervention-by-subgroup interaction as factors, and baseline(DB) NPI-C A+A total score as a covariate. Point estimate of the treatment difference and 2-sided 80% CI will be estimated using appropriate contrasts.

The analysis results (difference of LS means and 80% CI) of the different subgroups will be displayed in a forest plot.

Additionally, descriptive statistics of the actual values and the change from baseline(DB) to each postbaseline time point will be presented for NPIC A+A total score by intervention group and subgroup.

Similar subgroup analyses will be performed for the change in CMAI-C score. The results will be displayed in a forest plot.

The analyses will be performed for the Full analysis set.

5.5.11. Change in Care Settings

A listing of participants who have changed their care settings (community dwelling or assisted living) during the DB phase will be provided for the Full analysis set.

5.6. Safety Analyses

All safety analyses will be based on safety analysis set.

For all continuous safety variables, descriptive statistics by intervention group will include the N, mean, standard deviation, median, minimum, and maximum. Categorical variables will be summarized by intervention group using frequency counts and percentages.

5.6.1. Extent of Exposure

The number and percentage of participants who receive study intervention will be summarized.

Descriptive statistics for duration of study intervention (N, mean, SD, median, and range (minimum, maximum)) will be summarized.

Duration of intervention will be summarized in the following duration categories: <=7 days, 8-14 days, 9-21 days, 22-28 days, 29-35 days, 36-42 days, >42 days.

Study intervention duration is defined as (date of last dose of study intervention – date of first dose of study intervention) +1. Number of doses is defined as the total number of dose administrations, which is the total number of days that study intervention was administered to the participant (excluding days off study intervention).

The analysis will be performed on the safety analysis set.

5.6.1.1. Intervention Compliance

Compliance will be summarized descriptively for each study intervention.

The percent compliance will be categorized and the number and percentage of participants in each category will be summarized by intervention group for study agent.

Compliance will be calculated for the study intervention as:

Compliance (%) = (number of days where the expected number of tablets were taken)/(days expected to be dosed (includes days where the study intervention was not taken)) x 100

The analysis will be performed on the safety analysis set.

5.6.2. Adverse Events

The verbatim terms used in the CRF by investigators to identify adverse events will be coded using the Medical Dictionary for Regulatory Activities (MedDRA). Any AE occurring at or after the initial administration of study intervention through the day of last dose plus 2 days is considered to be treatment emergent. AEs with onset date > date of last dose of double-blind study intervention plus 2 days will be assigned to follow-up phase. If the event occurs on the day of the initial administration of study intervention taken is not entered as 'Not Applicable' in the database), then the event will be considered as treatment emergent. If the event date is recorded as partial or completely missing, then the event will be considered to be treatment emergent unless it is known to be prior to the first administration of study intervention based on partial onset date or resolution date. All reported adverse events will be included in the analysis. For each adverse event, the number and percentage of participants who experience at least 1 occurrence of the given event will be summarized by planned intervention group.

Summary tables will be provided for treatment-emergent adverse events:

- AEs (all AEs, and AEs with incidence of at least 5% in any treatment group)
- Serious AEs (SAEs)
- AEs leading to discontinuation of study intervention
- AEs by severity
- AEs by relationship to study intervention
- AEs of special interest (See Appendix 6.6 for list of adverse events in each category)

In addition to the summary tables, listings will be provided for participants who had:

- SAEs
- AEs leading to discontinuation of study intervention
- AEs of special interest

A listing of participants who died will be provided.

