- m. If the ICF for optional genetic and pharmacogenomic (DNA) research sample is signed, the sample should be collected at the specified time point; however, if necessary, it may be collected at a later time point without constituting a protocol deviation.
- n. Study intervention intake ends on the night of Day 42.
- o. Vital signs collection will be done only if an in-person site visit is conducted.
- p. An extension of up to 2 weeks of the screening phase may be allowed (eg, if needed to confirm eligibility criteria, taper off a sleep medication or for scheduling difficulties) with permission from the sponsor's medical monitor or designee. The minimal screening duration should be 2 weeks to allow the proper conduct of the BPST.
- q. Off-body touchless sensors (optional in the study) will be used in a subset of participants. The sensor(s) will be placed in the participants home and be used from screening to end of the study.
- r. The IWRS will assign medication for 4 weeks at D15 to cover up to D43.
- s. Screening visit 1 assessments can be split over 2 days, if needed, however they should be conducted no more than three days apart.
- t. In case of a positive result, one retest is allowed. Furthermore, if the test results contradict to the data obtained from the patient and caregiver, clinical judgement should be applied.

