8.5.1. Evaluations

Blood samples for the determination of plasma concentrations of seltorexant, its M12 metabolite,

and alpha-1-acid glycoprotein, will be collected from participants per the SoA.

In addition, blood samples will be collected for determination of plasma concentrations of seltorexant, its M12 metabolite, and alpha-1-acid glycoprotein in participants who discontinue study drug for an AE, have an AESI, or have an SAE if the sample can be obtained within 15 hours of the last study drug administration.

Blood samples will be collected to determine alpha-1-acid glycoprotein levels at each PK collection day (as indicated in the SoA) to calculate the unbound concentrations.

During the DB treatment phase, blood samples for PK will be collected from all participants, including placebo-treated participants, but samples from placebo-treated participants will not be analyzed for PK. These samples will be stored and may be analyzed if needed (eg, suspicion of an incorrect treatment assignment).

Additional information about the collection, handling, and shipment of biological samples can be found in the laboratory manual.

The exact date and time of PK blood sample collection must be recorded, along with all concomitant medications (dose, drug, start and stop date). Study drug dosing time on the day before each PK sample collection will be accurately recorded by exact dosing date and time by the participant or his study partner in the participant medication diary. In addition, in participants who have ongoing AE leading to discontinuation every effort will be made to collect additional PK sample.

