9.3. Populations for Analysis Sets

For purposes of analysis, the following analysis sets are defined:

Analysis Set	Description
Screened	All participants who sign the ICF
Randomized	All participants who were randomized in the study
Full	All randomized participants who take at least 1 dose of study intervention
Safety	All randomized participants who take at least 1 dose of study intervention.

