9.4.3. Safety Analyses

All safety analyses will be made on the Safety Analysis Set.

Adverse Events

The verbatim terms used in the eCRF by investigators to identify AEs will be coded using the Medical Dictionary for Regulatory Activities (MedDRA). Treatment-emergent adverse events are

AEs with onset during the DB treatment phase or that are a consequence of a pre-existing condition that has worsened since baseline. All reported treatment-emergent AEs will be included in the analysis. For each AE, the percentage of participants who experience at least 1 occurrence of the given event will be summarized by intervention group.

Summaries, listings, datasets, or participant narratives may be provided, as appropriate, for those participants who die, who discontinue intervention due to an AE, or who experience a severe or an SAE or an AESI.

Clinical Laboratory Tests

Laboratory data will be summarized by type of laboratory test. Reference ranges and markedly abnormal results (specified in the Statistical Analysis Plan) will be used in the summary of laboratory data. Descriptive statistics will be calculated for each laboratory analyte at baseline and for observed values and changes from baseline at each scheduled time point. Frequency tabulations of the laboratory abnormalities will be made. A listing of participants with any markedly abnormal laboratory results will be provided.

Electrocardiogram

The effects on ECG measurements (heart rate, PR interval, QT interval, and QTc interval) will be evaluated using descriptive statistics and frequency tabulations. QTc intervals will be calculated using the Bazett and Fridericia correction methods and summarized accordingly.

Descriptive statistics of QTc intervals and changes from baseline will be summarized at each scheduled time point. The percentage of participants with QTc interval higher than pre-specified levels will be summarized, as will the percentage of participants with QTc interval increases from baseline >30 milliseconds or >60 milliseconds.

A listing of participants with abnormal ECG findings will be presented.

Vital Signs

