10.4.4. Special Reporting Situations

Safety events of interest on a sponsor study intervention in an interventional study that may require

expedited reporting or safety evaluation include, but are not limited to:

- Overdose of a sponsor study intervention
- Suspected abuse/misuse of a sponsor study intervention
- Accidental or occupational exposure to a sponsor study intervention
- Medication error, intercepted medication error, or potential medication error involving a Johnson & Johnson medicinal product (with or without patient exposure to the Johnson & Johnson medicinal product, eg, product name confusion, product label confusion, intercepted prescribing or dispensing errors)
- Exposure to a sponsor study intervention from breastfeeding

Special reporting situations should be recorded in the eCRF. Any special reporting situation that meets the criteria of an SAE should be recorded on the SAE page of the eCRF.

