6.4. Appendix 4 Protocol Deviations

In general, the following list of major protocol deviations may have the potential to impact participants' rights, safety or well-being, or the integrity and/or result of the clinical study. Participants with major protocol deviations will be identified prior to database lock and the participants with major protocol deviations will be summarized by category for safety analysis sets.

- Developed withdrawal criteria but not withdrawn
- Entered but did not satisfy criteria
- Received a disallowed concomitant treatment
- Received wrong treatment or incorrect dose
- Other

Number of participants not meeting inclusion criteria, or meeting exclusion criteria will be summarized by study intervention group for the safety analysis set.

Additional analyses of protocol deviations for assessing and mitigating the impact of COVID-19 on study outcome are presented in Section 6.9.

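### Adverse events are grouped by planned treatment, so anyone who took the other arm's tablets is counted under a treatment they did not take

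*SAP*

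**What the plan says.** SAP 5.6.2 sets the column for adverse events by plan: "participants who experience at least 1 occurrence of the given event will be summarized by planned intervention group". Protocol 9.4.3 is less specific: "the percentage of participants who experience at least 1 occurrence of the given event will be summarized by intervention group". The SAP's laboratory tables (5.6.3.1) refer to the study intervention group without saying planned or received.

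The safety set in Protocol 9.3 is "All randomized participants who take at least 1 dose of study intervention", and SAP 4 agrees. The full analysis set has the same definition in both documents. Neither set has a rule that places a participant in the arm whose tablets they took.

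Both documents allow for wrong treatment. SAP 6.4 lists "Received wrong treatment or incorrect dose" among the major deviations. Protocol 8.5.1 says of placebo-arm blood samples that "samples from placebo-treated participants will not be analyzed for PK", but that the stored samples "may be analyzed if needed (eg, suspicion of an incorrect treatment assignment"). Protocol 10.4.4 gives "intercepted prescribing or dispensing errors" as examples of reportable medication errors.

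Study drug is dispensed twice, on Day 1 and Day 15. The Schedule of Activities notes: "The IWRS will assign medication for 4 weeks at D15 to cover up to D43".

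**The concern.** Planned grouping suits the efficacy analysis. A safety table is meant to show what happened to people who took the drug. If a placebo-randomised participant is found to have taken seltorexant, SAP 5.6.2 still puts their events in the placebo column; the reverse error puts placebo-exposed events in the seltorexant column. Where the drug raises the event rate, both errors move the difference toward zero, which is the unhelpful direction for safety.

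Section 5.6.2 also mixes two principles. It decides whether an event is treatment-emergent from actual dosing dates, but decides the column from the plan.

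Safety and tolerability are study objectives, and this is the first study of seltorexant in this population (Protocol 2.1). Protocol 2.3 says that few participants reported the known drug reactions at the doses planned here, so single cases can matter in the tables.

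**Working it through.** **Arm size.** Protocol 9.2 and SAP 3 give 86 participants randomised 1:1, so 86/2 = 43 per arm. As a check on that figure: a difference of 5, SD 10, one-sided alpha 0.1 and 80% power give 2 × [10 × (1.2816 + 0.8416)/5]² = 36.06 per arm. Doubled and divided by 0.85 for 15% dropout, this is 72.13/0.85 = 84.9, which is 86 when rounded up to an even number. With 43 × 0.85 per arm, power is 80.4%. The stated size reproduces.

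**Who is misclassified.**
- Placebo-randomised, took seltorexant: drug-exposed events go in the placebo column.
- Seltorexant-randomised, took placebo: placebo-exposed events go in the seltorexant column.
- Wrong kit from the same arm, or incorrect dose within the seltorexant arm: nothing changes column.

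**Expected effect.** Let k participants in an arm of 43 take the other arm's tablets throughout. The expected rate in that column is [(43 − k) × p_own + k × p_other]/43, so the difference shrinks by k × (p_drug − p_placebo)/43. The documents give neither event rates for this population nor an error rate. The rates and k below are assumptions.

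| Assumed true rates (drug vs placebo) | True difference | k = 1, one way | k = 4, one way | k = 1 in each arm | k = 4 in each arm |
|---|---|---|---|---|---|
| 10% vs 2% | 8.0 | 7.8 | 7.3 | 7.6 | 6.5 |
| 20% vs 5% | 15.0 | 14.7 | 13.6 | 14.3 | 12.2 |

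Worked example, 20% vs 5%, one placebo-randomised participant given seltorexant: the placebo column becomes (42 × 5% + 20%)/43 = 5.35%, and the difference 14.65 points. The loss is 15/43 = 0.35 points. For 10% vs 2% it is 8/43 = 0.19 points. Four one-way errors cost 0.74 to 1.40 points.

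**Where one case can show.** SAP 5.6.2 plans a table of events with incidence of at least 5% in any group. Suppose two seltorexant participants and one placebo-randomised participant who took seltorexant all have somnolence. By plan this is 2/43 = 4.7% against 1/43 = 2.3%, so the event is left out of that table. As received it is 3/44 = 6.8% against 0/42, so it is included. The table of all events would show it either way. This case is constructed.

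**Mixed exposure.** Dosing runs from Day 1 to Day 42, with a second dispensing at Day 15. A placebo-randomised participant wrongly given seltorexant at Day 1 only would take it for about 14 of 42 nights. A rule that assigns people to the treatment taken on most dosing days would leave this participant under placebo, so the grouping rule must deal with mixed exposure explicitly.

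**The case against.** The strongest case against acting is that nothing is shown to have gone wrong. The IWRS assigns a treatment code and a matching kit (Protocol 6.3), study drug may not be reassigned to another participant (Protocol 6.2), and no cross-arm error is reported in either document. Wrong-treatment deviations are identified before database lock and summarised for the safety set (SAP 6.4). Listings are planned for serious events, events of special interest, events leading to discontinuation, and deaths (SAP 5.6.2). Adverse event summaries are descriptive, so no test is distorted. All of this stands, and it keeps the point minor. It does not supply a table by treatment received.

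A reader might draw four stronger conclusions that the documents do not support.
- That any dispensing error puts drug events in the placebo column. Only a placebo-randomised participant who takes seltorexant does this.
- That each error costs 2.3 points. The figure 1/43 = 2.3% is one participant's weight in an arm, and it applies only if that participant has the event.
- That the stored placebo samples are a check for errors. Protocol 8.5.1 allows their assay once there is suspicion. The mis-stratification recorded in the SAP version history concerns stratum values and is not evidence of misdispensing.
- That all safety tables are by plan. Only the adverse event sentence says planned; the others leave it open.

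**Conclusion.** The point holds as a minor one. SAP 5.6.2 states a planned-treatment rule for adverse events, and for a participant who took the other arm's tablets that rule counts events under a treatment not taken. Where the drug raises the rate, the bias is toward no difference. Its size is zero without a cross-arm error. Otherwise it is about 0.2 to 0.35 points in the expected difference per misdispensed participant, assuming 43 per arm, wrong tablets for the whole period, and true rates of 10% vs 2% or 20% vs 5%. How many such errors occurred cannot be judged from the documents.

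**What to change.** In SAP 4, 5.6 and 5.6.2, state that all safety tables group participants by treatment actually received, and that anyone who took at least one dose of seltorexant is counted in the seltorexant group. Use this in preference to a most-dosing-days rule. Add a listing of participants whose planned and received treatments differ. Keep planned treatment for the full analysis set.

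The cost is a few sentences, one derived variable and one listing. There is a small downside: for participants with mixed exposure, some events that occurred on placebo will be counted under seltorexant. If no cross-arm error occurred, the adverse event tables do not change.
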